#### Substudies

Three optional longitudinal substudies will be completed within this study in subsets of consenting participants, as follows:

- An amyloid PET substudy involving assessments of amyloid by PET scan at Screening and at Weeks 78 and 104
- A tau PET substudy involving assessments of tau by PET scan at Screening and at Weeks 78 and 104

For participants of these substudies, study-specific procedures are required for provision of baseline PET scans

# 5.2. Study Duration for Participants

The total duration of the study for each participant will be approximately 130 weeks, including a series of screening visits within 8 weeks before administration of the first dose, and a 104-week placebo-controlled treatment period. Additionally, participants will undergo a safety FU Visit 18 weeks after the final dose of aducanumab.

Participants will have approximately 39 scheduled clinic visits, 27 of which are dosing visits, as well as up to 8 telephone safety FU contacts, as follows:

- Screening Visits 1 to 3 will occur no more than 60 days before the first dose of study treatment on Day 1. Visits will be conducted on multiple days. All screening procedures should be completed within 60 days; however, with Sponsor approval, the overall screening period may be extended up to 90 days in the event of logistical issues related to PET scans (and/or due to other major causes [i.e., institutional restrictions or participant disposition due to COVID-19 or other major disasters/disruptions]). These screening visits will include baseline brain MRI, clinical scales of cognition and function, biological fluid sampling (including CSF), amyloid and tau PET scans (where available), physical and neurological examinations, and all other safety and efficacy assessments. See Section 1.3 for the Schedules of Activities.
- Twenty-seven dosing visits (Day 1 and Weeks 4, 8, 12, 16, 20, 24, 28, 32, 36, 40, 44, 48, 52, 56, 60, 64, 68, 72, 76, 80, 84, 88, 92, 96, 100, and 104).

- Eight telephone safety FU contacts after each of the first 8 doses.
- Four visits separate from dosing for clinical functional and cognitive assessments (Weeks 26, 50, 78, and 106).
- One safety FU visit at Week 122, 18 weeks after the last dose at Week 104, or 18 weeks after administration of the last dose for participants who discontinue treatment early.
- A minimum of 6 MRI visits, with 4 during treatment (Week 14 [before escalation to 6 mg/kg, before at the fifth dose], Week 22 [before escalation to 10 mg/kg, before the seventh dose], Week 30 [before the third dose at 10mg/kg], and Week 42 [before the sixth dose at 10 mg/kg]. Two additional MRIs will be performed at Week 106 and at Week 122 [EOS] 18 weeks after the final-dose safety FU) or 18 weeks after administration of the last dose for participants who discontinue treatment early.

# 5.3. Monitoring and Management of ARIA

## 5.3.1. Dose Suspension or Permanent Discontinuation for ARIA Events

Guidelines on the management and disposition of ARIA cases (including the criteria to be met for the continuation, suspension/resumption, permanent discontinuation of dosing due to ARIA, resumption of dosing after dose suspension due to ARIA [including rules for titrating up to the assigned dose], and management of recurrent ARIA) are provided in the following subsections.

The central MRI reading center will report incident cases of ARIA-E and ARIA-H to both the Sponsor and the Investigator within a specified time after observing the finding on MRI per the imaging manual procedures, with an assessment of severity. All cases of ARIA must be reviewed by the Investigator; decisions on dosing continuation, interruption, or discontinuation will be based on the Investigator's clinical assessment of the participant and the MRI information provided by the central reader. Dosing may also be terminated at the discretion of the Sponsor for medical reasons.

If a participant experiences symptoms that could be suggestive of ARIA, clinical evaluation should be performed, including MRI testing if indicated.

See Section 8.1 for the full list of criteria for discontinuing study treatment.

#### 5.3.1.1. ARIA-E

**Table 4:** Disposition of ARIA-E Cases

Clinical	ARIA-E Severity on MRI (Central Read)			
Symptom Severity 	Mild	Moderate	Severe	
Asymptomatic	Continue dosing at current dose and	Suspend dosing. Once ARIA-E resolves, the participant may resume dosing at the same dose.		
Mild	schedule	Suspend dosing. Once ARIA-E and clinical symptoms resolve, the participant may resume dosing at the same dose.		
Moderate	Suspend dosing. Once ARIA-E and clinical symptoms resolve, the participant may resume dosin			
Severe	at the same dose.			

<sup>1 Nonserious symptoms only. If serious symptoms of ARIA-E (according to the definition of serious adverse events in Section 11.1.2), treatment should be permanently discontinued.

The following study activities must be followed for participants with ARIA-E:

• Participants with ARIA-E should complete all scheduled clinic visits for assessments and, in addition, have an unscheduled visit for an MRI every 4 weeks (± 5 days) until the ARIA-E has resolved per the centrally read MRI. In addition, and PK samples will be collected at the first visit, scheduled or unscheduled, following an episode of ARIA-E.

For nonserious ARIA-E and ARIA-E with nonserious symptoms (according to the definition of serious adverse events in Section 11.1.2):

- Participants who develop ARIA-E that is radiographically mild, per central MRI reading, and who have no symptoms or symptoms that are mild may continue dosing per protocol. Participants should complete all scheduled clinic visits for assessments and have an unscheduled visit for an MRI Q4W (± 5 days) until the ARIA-E has resolved per the centrally read MRI.
  - If moderate or severe symptoms develop during follow-up of the ARIA-E event, dosing should be suspended.
  - If a follow-up MRI demonstrates radiographically moderate or severe ARIA-E, per central MRI reading, dosing should be suspended.

If dosing is suspended, once the ARIA-E has resolved per the centrally read MRI and once the clinical symptoms have resolved (in the Investigator's opinion), the participant may resume treatment at the same dose (see Section 5.3.1.6 for dose resumption rules).

• Participants who develop ARIA-E that is radiographically mild, per central MRI reading, accompanied by moderate or severe clinical symptoms, should suspend dosing. Once the ARIA-E has resolved per the centrally read MRI and once the clinical

symptoms have resolved (in the Investigator's opinion), the participant may resume treatment at the same dose. See Section 5.3.1.6 for dose resumption rules.

• Participants who develop **ARIA-E** that is radiographically moderate or severe, per central MRI reading, with or without symptoms, should suspend dosing. Dosing may be resumed at the same dose once the ARIA-E has resolved per the centrally read MRI and once the clinical symptoms, if any, have resolved (in the Investigator's opinion). See Section 5.3.1.6 for dose resumption rules.

For serious ARIA-E events or ARIA-E events with serious symptoms (according to the definition of serious adverse events in Section 11.1.2):

• Participants who develop ARIA-E (of any radiographic severity) that is considered serious or that is accompanied by serious clinical symptoms (according to the definition of serious adverse events in Section 11.1.2), at any time during the study, should permanently discontinue treatment.

See Section 5.3.1.6 for details on resumption of dosing when suspension occurs during the titration period and Section 5.3.1.7 for guidelines on resuming dosing after a recurrence of ARIA.

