- Participants who develop between 5 and 9 (≥ 5 and ≤ 9) treatment-emergent microhemorrhages (moderate radiographic per central MRI reading), with or without symptoms of any severity, should suspend dosing. Dosing may be resumed at the same dose once the ARIA-H is radiographically stable on follow-up MRI and clinical symptoms, if any, have resolved (in the Investigator's opinion). See Section 5.3.1.6 for dose resumption rules.
- Participants who develop 10 or more (≥ 10) treatment-emergent microhemorrhages (severe radiographic per central MRI reading), should permanently discontinue treatment.

For serious ARIA-H microhemorrhages or ARIA-H microhemorrhages with serious symptoms (according to the definition of serious adverse events in Section 11.1.2):

Participants who develop ARIA-H microhemorrhage (of any radiographic severity) that
is accompanied by serious clinical symptoms (according to the definition of serious
adverse events in Section 11.1.2) should permanently discontinue treatment.

See Section 5.3.1.6 for details on resumption of dosing when suspension occurs during the titration period and Section 5.3.1.7 for guidelines on resuming dosing after a recurrence of ARIA.

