# 8. DISCONTINUATION OF STUDY TREATMENT AND/OR WITHDRAWAL OF PARTICIPANTS FROM THE STUDY

# 8.1. Discontinuation of Study Treatment

A participant *must* permanently discontinue aducanumab for any of the following reasons:

- The participant develops any new acute or subacute hemorrhage.
- The participant develops any treatment-emergent incident of cerebral hemorrhage > 1 cm in diameter on T2\* sequence.
- The participant develops a radiographically severe ARIA-H (10 or more treatmentemergent microhemorrhage or more than 2 treatment-emergent superficial siderosis)
- The participant develops any radiographic type of ARIA- E or ARIA-H accompanied by serious symptoms (according to the definition of serious adverse events in Section 11.1.2).
- The participant develops a cortical infarct (defined as > 1.5 cm in diameter irrespective of anatomic location).
- The participant develops more than 1 > 1 lacunar infarct (defined as  $\leq 1.5$  cm in diameter).
- The participant withdraws consent to continue study treatment.
- The participant experiences a medical emergency that necessitates permanent discontinuation of study treatment or unblinding of the participant's treatment assignment.
- The participant experiences an AE that necessitates treatment discontinuation or requires continued treatment that meets exclusionary criteria.
- The participant experiences a severe infusion reaction.
- The participant initiates treatment of Alzheimer's disease with a commercially available disease-modifying drug.
- At the discretion of the Investigator for medical reasons, including treatment-emergent ARIA events.
- At the discretion of the Sponsor for safety or other reasons.
- At the discretion of the Investigator or Sponsor for noncompliance.
- The participant becomes pregnant; study treatment must be discontinued immediately, and pregnancy must be reported according to protocol instructions.

The primary reason for discontinuation of study treatment must be recorded in the participant's CRF.

Participants who discontinue treatment are encouraged to remain in the study, attend a safety FU Visit 18 weeks after the last dose of study treatment, and immediately continue protocol required tests and assessments at a subset of the clinic visits (see Table 3) until the end of the study per the Schedule of Activities or until the participant withdraws consent.

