#### 11.1.2. Serious Adverse Event

An SAE is any untoward medical occurrence that at any dose:

- Results in death.
- In the view of the Investigator, places the participant at immediate risk of death (a life-threatening event); however, this does not include an event that, had it occurred in a more severe form, might have caused death.
- Requires inpatient hospitalization or prolongation of existing hospitalization.
- Results in persistent or significant disability/incapacity.

- Results in a congenital anomaly/birth defect.
- Is a medically important event.

A medically important event is an AE that, in the opinion of the Investigator, may jeopardize the participant or may require intervention to prevent one of the other outcomes listed in the definition above. (Examples of such medical events include allergic bronchospasm requiring intensive treatment in an emergency room or convulsions occurring at home that do not require an inpatient hospitalization.)

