Study Procedures (Study Procedures (not safety not efficacy related)	Participant is eligible per malignancy exceptions noted in the protocol but the SAF was submitted for review retrospectively.	Minor
Study Procedures (Study Procedures (not safety not efficacy related)	Baseline tau PET scan not done for participant at a mandatory tau site	Minor
Exclusion criteria	Participant has been randomized and received first dose of study medication but used allowed chronic concomitant medications at doses that were not been stable for at least 4 weeks prior to Screening Visit 1 and during Screening up to Day 1, or used Alzheimer's disease medications at doses that were not stable for at least 8 weeks prior to Screening 1 up to Day 1 or used allowed chronic	Major

Deviation Category	Deviation Description	Severity Classification
3 1	concomitant medications that affect cognition at doses that were not stable for at least 8 weeks prior to screening Visit 1 and during screening up to Day 1.	
Randomization	Subject enrolled (for treatment) in IXRS but not treated	Major
Randomization	Subject randomized to wrong arm due to mis-entry of ApoE ε4 carrier status.	Major
IP administration	Wrong study drug dispensed	Major
IP administration	Subject received IP despite meeting discontinuation or withdrawal criteria	Major
IP administration	Missed infusion not due to ARIA	Major
Efficacy	CDR, ADCS-ADL-MCI, ADAS-Cog 13, MMSE, NPI-10 not administered SM may record one PD at the visit level, including all the assessments, as long as there is no difference in the category or severity. A second PD should be included for minor assessments missed at the same visit.	Major
Study Procedures (Study Procedures (not safety not efficacy related)	Any individual procedure not conducted per protocol requirements (either skipped or out of window) except those noted in the note. SM may record one PD at the visit level, including all the assessments, as long as there is no difference in the category or severity. NOTE: Does not apply to MRI, Infusions, CDR, ADCS-ADL-MCI, ADAS-Cog 13, MMSE, NPI-10, C-SSRS and labs, which, if missed, are considered major PD per this classification document	Minor
Safety	Participant dosed based on local read of MRI rather than central read as required by protocol	Major
Safety	MRI visit or individual MRI not done (scheduled or unscheduled ARIA visit)	Major / potentially critical

Deviation Category	Deviation Description	Severity Classification

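### ARIA-E judged serious but without serious symptoms: the text of Protocol 5.3.1.1 stops treatment permanently, while Table 4 lets dosing continue or resume and the ARIA criterion in 8.1 is silent; the ARIA-H rules have a related gap

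*Protocol*

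**What the plan says.** The text of Protocol 5.3.1.1 puts its suspend-and-resume rules under a sub-heading for nonserious ARIA-E. A second sub-heading follows: "For serious ARIA-E events or ARIA-E events with serious symptoms (according to the definition of serious adverse events in Section 11.1.2"). The rule beneath it permanently discontinues "Participants who develop ARIA-E (of any radiographic severity) that is considered serious or that is accompanied by serious clinical symptoms".

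Table 4, in the same section, sets disposition by MRI severity and symptom severity. With no symptoms, dosing continues if the MRI finding is mild. If it is moderate or severe, the entry is "Suspend dosing. Once ARIA-E resolves, the participant may resume dosing at the same dose". The footnote limits the table to nonserious symptoms and requires permanent discontinuation for serious ones. It does not mention an event that is serious in its own right.

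Section 5.3.1 directs the reader onward: "See Section 8.1 for the full list of criteria for discontinuing study treatment". The criterion in 8.1 that covers both ARIA-E and ARIA-H applies when they are "accompanied by serious symptoms (according to the definition of serious adverse events in Section 11.1.2"). Section 8.1 also lists radiographically severe ARIA-H, adverse events that necessitate stopping, Investigator discretion (which expressly includes ARIA) and Sponsor discretion.

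For ARIA-H microhemorrhage, the sub-heading in 5.3.1.2 reads "For serious ARIA-H microhemorrhages or ARIA-H microhemorrhages with serious symptoms", but the bullet under it covers only serious clinical symptoms. Section 5.3.1.3 does the same for superficial siderosis.

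One of the seriousness criteria in 11.1.2 is "Is a medically important event", which is left to the Investigator's opinion.

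**The concern.** Permanent discontinuation ends a participant's treatment for good, and ARIA is the most common safety finding the protocol reports for this drug. The condition that triggers the stop should read the same in the text, in the table a site is likely to consult, and in the section named as the complete list. Here one ground, the seriousness of the event itself, appears in the text of 5.3.1.1 and is missing from the other two.

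The difference carries into the report. SAP 9.2, Table 11, grades as Major the case "Subject received IP despite meeting discontinuation or withdrawal criteria", and also grades as Major a failure to follow the ARIA dosing rules. Whether re-dosing such a participant counts as a Major deviation therefore depends on which passage is taken as the criterion. SAP 5.7.1.4 also summarizes ARIA leading to discontinuation separately, on the ground that the protocol sometimes required it; for this case, whether it was required is unclear.

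**Working it through.** No figure in the plan needs reproducing. The check sets the passages side by side.

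**Step 1: can the case occur?** Section 11.1.2 needs no symptom for an event to be medically important. Protocol 11.3.2 treats radiographic ARIA as an adverse event of special interest in its own right and provides for it to qualify as an SAE. SAP 5.7.1.5, Table 4, has a fixed term for asymptomatic ARIA-E, and the adverse event listing in SAP 5.7.1.1 carries seriousness as a separate field. The combination is possible and can be recorded.

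**Step 2: worked case for ARIA-E.** Take a participant with no symptoms whose ARIA-E is judged serious as medically important.

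| Source | Mild on MRI | Moderate or severe on MRI |
|---|---|---|
| 5.3.1.1 text, serious events | Permanent discontinuation | Permanent discontinuation |
| Table 4, asymptomatic row and footnote | Continue | Suspend; may resume after resolution |
| 8.1, ARIA criterion | Not met | Not met |
| 8.1, general AE and discretion criteria | Stopping permitted, not required by seriousness | Same |

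The first two rows disagree in both columns.

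**Step 3: ARIA-H.** Take serious ARIA-H without symptoms. The headings in 5.3.1.2 and 5.3.1.3 announce a rule for it and the bullets give none. Tables 5 and 6 say continue if mild, and suspend with possible resumption if moderate. Radiographically severe ARIA-H is discontinued everywhere, so the gap is limited to mild and moderate cases.

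**Step 4: deviations.** Re-dosing the participant in Step 2 complies with Table 4 and breaches the 5.3.1.1 text, so it can fall under the Major rows of SAP Table 11. Stopping permanently in the moderate or severe case breaches nothing, because Table 4 only permits resumption. In the mild case the table's wording is directive, but the corresponding text in 5.3.1.1 says dosing may continue, and 8.1 allows discretion.

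**Step 5: size.** The documents do not give the share of ARIA-E that is serious without serious symptoms. For scale only:
- SAP 2.2.3 reports over 1000 enrolled. At 1000 and 2:1 randomization, 1000 × 2/3 = 667 are on aducanumab.
- Earlier Phase 3 figures in the protocol give ARIA-E in 35.2% and symptoms with ARIA in 10.0% of the 10 mg/kg group. As a rough guide, 35.2% − 10.0% = 25.2% had ARIA-E without symptoms; this is approximate because the 10.0% covers any ARIA. Then 667 × 0.252 = 168.
- If 1% to 5% of these were judged serious (an assumption), 168 × 0.01 to 168 × 0.05 is about 2 to 8 participants.
- On the planned 1512: 1008 × 0.252 = 254, giving about 3 to 13.

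The true share could be near zero, and early termination cut exposure short.

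**The case against.** The best reply is that the text of 5.3.1.1, read in full, gives one answer. The suspend-and-resume bullets sit under a heading for nonserious ARIA-E, serious events have their own heading, and dosing decisions rest on the Investigator's clinical assessment. An Investigator who judges an asymptomatic finding serious may already stop treatment. This is correct for the text, but it does not bring Table 4 and the ARIA criterion in 8.1 into line with it. Discretion to stop is also different from a requirement to stop.

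A reader might go further in four ways that the documents do not support:

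- That 8.1 ends treatment for ARIA only when symptoms are serious. It also lists severe ARIA-H, a general adverse event criterion, and Investigator and Sponsor discretion, and nothing in it directs re-dosing. Permission to resume comes from Table 4.
- That stopping and re-dosing would each be a Major deviation. In the moderate or severe case only re-dosing clearly breaches a stated rule.
- That sites will in fact decide differently, or that a known number of participants is affected. The documents show that the passages conflict; they give no evidence of practice and no count.
- That the SAP is wrong not to split ARIA discontinuations by ground. The planned listing already carries seriousness, ARIA symptom status and action on treatment, and SAP Table 5 includes serious and severe ARIA. A split is a preference.

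It is also fair to say that dosing was offered only until 1 May 2024, so rewording the protocol now serves mainly the record and any reuse of the text.

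**Conclusion.** The inconsistency is real and rests on wording alone. For ARIA-E that is serious without serious symptoms, the text of 5.3.1.1 requires a permanent stop, Table 4 allows dosing to continue or resume, and the ARIA criterion in 8.1 does not apply. For mild or moderate ARIA-H of the same kind, the sections announce a rule and do not give one. The conclusion assumes only that an event can be serious by medical importance without serious symptoms, which 11.1.2 allows.

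The number affected is unknown and probably small; the range of about 2 to 8 depends on an assumed 1% to 5%, and the finding does not depend on it. The consequence is an unclear rule for an irreversible dosing decision and an unclear basis for classifying re-dosing as a Major deviation. No statistical test is affected, since the SAP plans none. The passages must be reconciled, and the choice of rule is for the sponsor.

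**What to change.** Make seven places in the protocol state the same condition for ARIA that is serious without serious symptoms: the 5.3.1.1 text, the footnotes to Tables 4, 5 and 6, the serious-event bullets in 5.3.1.2 and 5.3.1.3, and the ARIA criterion in 8.1. If the table rows are meant to exclude such events, say so there.

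Before database lock, record which condition is used when the ARIA dosing and discontinuation rows of SAP Table 11 are classified, and apply it to every such case.

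The cost is wording in seven places and one documented classification rule, with no new assessments or data. Splitting the ARIA discontinuation summary in SAP 5.7.1.4 by ground is optional and not needed to correct the error.

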# 5.3.1.2. ARIA-H (Microhemorrhage)

Treatment-emergent microhemorrhages are defined as microhemorrhages that occur while the participant is on study treatment and do not include microhemorrhages at baseline.

Table 5:	Disposition	of ARIA-H	(Microhemo	rrhage) Cases
I abic 5.	DISDUSITION	UI I XIXII XII X		mazer Cases

Clinical	Treatment-emergent Microhemorrhages (Central Read		
Symptom	Mild Moderate		Severe
Severity 	≥ 1 and ≤ 4	≥ 5 and ≤ 9	≥10
Asymptomatic	Continue dosing at current schedule	Suspend dosing. Once ARIA-H is stable, the participant may resume dosing at the same dose.	Permanently discontinue
Symptomatic	Suspend dosing. Once ARIA-H stabilizes and clinical symptoms resolve, the participant may resume dosing at the same dose.		treatment

<sup>1 Nonserious symptoms only. If serious symptoms of ARIA-H (according to the definition of serious adverse events in Section 11.1.2), treatment should be permanently discontinued.

The following study activities must be followed for participants with ARIA-H (microhemorrhage):

• Participants with ARIA-H microhemorrhage should complete all scheduled clinic visits for assessments. In addition, if ARIA-H microhemorrhage is radiographically moderate, or if symptoms are present, participants should have an unscheduled visit for an MRI every 4 weeks (± 5 days) until the ARIA-H has stabilized per the centrally read MRI.

ARIA stabilization is defined as no change or a decrease in the number or size of microhemorrhages on 2 consecutive MRIs, including the initial detection MRI. In addition, and PK samples will be collected at the first visit, scheduled or unscheduled, following an episode of ARIA.

For nonserious ARIA-H microhemorrhages and ARIA-H microhemorrhages with nonserious symptoms (according to the definition of serious adverse events in Section 11.1.2):

- Participants who develop between 1 and 4 (≥ 1 and ≤ 4) treatment-emergent microhemorrhages (mild radiographic per central MRI reading), and who have no symptoms may continue dosing per protocol.
- Participants who develop between 1 and 4 (≥ 1 and ≤ 4) treatment-emergent microhemorrhages (mild radiographic per central MRI reading), accompanied by clinical symptoms of any severity, should suspend dosing. Dosing may be resumed at the same dose once the ARIA-H is radiographically stable on follow-up MRI and clinical symptoms have resolved (in the Investigator's opinion). See Section 5.3.1.6 for dose resumption rules.
- Participants who develop between 5 and 9 (≥ 5 and ≤ 9) treatment-emergent microhemorrhages (moderate radiographic per central MRI reading), with or without symptoms of any severity, should suspend dosing. Dosing may be resumed at the same dose once the ARIA-H is radiographically stable on follow-up MRI and clinical symptoms, if any, have resolved (in the Investigator's opinion). See Section 5.3.1.6 for dose resumption rules.
- Participants who develop 10 or more (≥ 10) treatment-emergent microhemorrhages (severe radiographic per central MRI reading), should permanently discontinue treatment.

For serious ARIA-H microhemorrhages or ARIA-H microhemorrhages with serious symptoms (according to the definition of serious adverse events in Section 11.1.2):

Participants who develop ARIA-H microhemorrhage (of any radiographic severity) that
is accompanied by serious clinical symptoms (according to the definition of serious
adverse events in Section 11.1.2) should permanently discontinue treatment.

See Section 5.3.1.6 for details on resumption of dosing when suspension occurs during the titration period and Section 5.3.1.7 for guidelines on resuming dosing after a recurrence of ARIA.

